5.3.2 PREPARING THE SUBJECT FOR DEVICE OPERATION

After the device is prepared for operation, the Investigator or qualified designated study personnel will prepare the subject for device operation by referencing the Instructions for Use (IFU) manual and following the steps outlined below. The subject will be placed in a supine or sitting position after the device is prepared for operation and maintain this position through observation.

- S9. Clean the subject's skin on his or her left wrist.
- S10. Take the small white connector/electrode array and remove the transparent plastic film attached to the electrodes to expose the adhesive. Place the small white connector/electrode array on the dorsal (top) of the subject's left wrist. The white connector shall be pointed medially (inward) towards the subject's body.
- S11. Take the large blue connector/electrode array and remove the transparent plastic film attached to the electrode to expose the adhesive. Place the large blue connector/electrode array on the left side of the neck's base and down across the front of the shoulder (above the clavicle). The blue connector shall point away from the neck, extending toward the direction of the left shoulder.
- S12. Place the wrist cuff on the subject's left wrist (above or over the top of the white electrode array), with the trunk cable connection pointing up the arm, and secure the wrist strap around the left wrist. The cuff should be snug with no gap between the wrist cuff and skin. The wrist cuff should not be able to slide or rotate on the wrist nor should it be too tight or restricting of blood flow.
- S13. Place the PPG finger glove on the subject's left digitus II manus (Index) fingertip. The white cable/top side of the finger glove should be on the dorsal (top) side of the finger. The fingertip shall be touching the end of the inside of the glove. Fingernails will often protrude through the end of the finger glove, which is normal.
- S14. Examine the trunk cable to ensure that it is connected securely to the CM-1500 display monitor and the wrist cuff.

CONFIDENTIAL Page 13 of 24

Z NEX

CLINICAL PROTOCOL

SPONSOR: ZMS

PROTOCOL: ZMS-1500-2021-Dialysis

S15. Connect both CM-1500 electrode array sets to the corresponding electrode lead cables protruding from the wrist cuff. The blue lead cable connector on the wrist cuff. The white connector/electrode array shall connect to the white lead cable connector on the wrist cuff. The lead cable connectors are shaped to match the electrode connectors- ensure connectors are properly aligned before inserting (DO NOT FORCE THE CONNECTION).

5.3.3 CM-1500 MONITORING SESSION

The Investigator or designated study personnel will operate the device by referencing the Instructions for Use (IFU) manual and following the study-specific steps outlined below.

- S16. Start the monitoring session by pressing "START" on the CM-1500 display monitor/monitoring screen. A message will appear informing the user that the monitoring session is in progress and the patient's baseline is being established. The device will begin to measure all five (5) parameters.
- S17. As monitoring continues, the display will show ECG and PPG pulse waveforms along with the Relative Index graph over time. Baseline measurements, for all parameters, are taken at the beginning of the monitoring session

 The subject should be relaxed during baseline establishment. The subject should remain in a supine or sitting position. The baseline measurement will continue for a minimum of 5 minutes.
- S19. Continue the monitoring session during the hemodialysis session. Upon completion of the session,

 continue the monitoring for a minimum of ten (10) minutes.

 If the subject needs to move to a different location during the 10-minute post-hemodialysis monitoring period, the time of movement should be noted on the CRF.
- S20. After the observation period has passed, "STOP" shall be pressed to end the monitoring session. The user will need to press "Yes" on the confirmation window to stop the monitoring session after pressing "STOP".
- S21. Document any observations or adverse events that occur throughout the entirety of the monitoring session.
- S22. After the monitoring session is stopped, remove the electrode array sets from the subject and dispose of the electrodes and wrist strap per site guidelines. Wipe down wrist cuff and cables per the IFU for next subject use.

SPONSOR: ZMS

PROTOCOL: ZMS-1500-2021-Dialysis

5.4 REPEAT STUDY PROCEDURES AND STUDY COMPLETION

Subjects will continue to be monitored at each of their next two (2) subsequent hemodialysis sessions. If the device is not available or the subject is unable to complete the monitoring session at the following hemodialysis session, the next available hemodialysis session will be acceptable, and the date of the last procedure and number of hemodialysis sessions in between monitoring sessions will be captured on the case report form. All attempts should be made to complete the subject's participation in the study within two (2) weeks of enrollment.

For the remaining two monitoring sessions, the procedure will continue the same as previously performed. After the third CM-1500 monitoring session is complete, the subject's participation in the study is considered complete. If the subject elects to withdraw from the study before completing their third monitoring session, or if 30 days have passed since the initial monitoring session, subject withdrawal will be captured on the case report form. Additional subjects will be enrolled (up to 20) until 15 complete data sets of three (3) monitoring sessions each have been complete.

5.5 ADVERSE EVENTS

Adverse Events (AE), Serious Adverse Events (SAE), or Unanticipated Adverse Device Effect (UADE) that occur after informed consent and before completion of the study will be recorded. SAE's may require follow-up contact via a telephone call, depending on the nature of the SAE.

6 DEVICE MANAGEMENT

6.1 UNPACKING AND INSPECTION

It is the responsibility of the Principal Investigator (PI) to ensure that all study devices are unpacked and inspected prior to using in any study procedures. Upon arrival, the Investigator or designated study personnel will remove the device display monitor and accessories from the shipping container; ensure all device components are received. The study site must inform the Sponsor of any missing or damaged items within seven (7) days. Devices with any missing or damaged items cannot be used and shall be replaced.

6.2 ACCOUNTABILITY, STORAGE & DISPENSATION

It is the responsibility of the Principal Investigator to ensure all study devices are inventoried and accounted for. The Investigator or qualified designated study personnel will record all information on the Device Accountability forms maintained in the Investigator Site Files (ISF).

The investigational device will be stored at the study center. When not in use, the device will be stored in a secure location (i.e., area with limited access or in a locked cabinet) under appropriate environmental conditions found in the Instructions for Use (IFU) manual.

The study device shall only be used under the supervision of the Principal Investigator or designated study personnel on authorized study subjects.

6.3 CLEANING & RETURN

The study device shall be cleaned before each use. Cleaning procedures will be followed per the Instructions for Use (IFU) manual and institutional procedures. The device should always be turned off

SPONSOR: ZMS

PROTOCOL: ZMS-1500-2021-Dialysis

and disconnected before cleaning. The study device and any unused accessories shall be returned to the Sponsor after study completion.

7 RISKS & BENEFITS

7.1 RISK DETERMINITATION & REDUCTION

This study is determined to be exempt and non-significant risk. An Investigational Device Exemption will not be submitted based on this determination.

Study subjects are subject to risk no greater than or similar to risks associated with undergoing a hemodialysis procedure. The study device and use of the device do not meet the definition of significant risk under 21CRF 812.3 (m). All adverse events will be recorded and analyzed to evaluate their significance. Possible risks may include:

- [Possible, Rare] Skin irritation or discomfort could occur from the electrodes
- [Possible, Mild] Discomfort could occur due to lying in a supine position for duration of the hemodialysis procedure.

Every possible effort will be made to reduce the risks to a minimum. Investigators or qualified designated study personnel will be experienced and skilled in performing hemodialysis procedures, receive training on the protocol and use of the device. All adverse events will be documented and reported to the Sponsor.

7.2 BENEFITS

This study is for research purposes only. There is no direct benefit to subjects participating in the study. Information from this study may help other people in the future.

8 SAFETY ASSESSMENT AND MANAGEMENT

Safety will be assessed by reviewing and summarizing adverse events.

8.1 SAFETY DEFINITIONS

8.1.1 ADVERSE EVENT (AE)

An Adverse Event (AE) is defined as any untoward medical occurrence, whether or not related to the study device or study procedure. AE's are characterized by grading, actions taken, relationship to hemodialysis procedure or study procedure, and outcome. These definitions are in the corresponding tables below. All adverse events related to the hemodialysis procedure will be recorded and reported in addition to those that may occur specific to the protocol-defined study procedure. All attempts should be made to ensure resolution of the adverse event upon study completion.

SPONSOR: ZMS

PROTOCOL: ZMS-1500-2021-Dialysis

Table 1: Adverse Event Severity Grading

Severity	Description
Grade 1: Mild	Awareness of signs or symptoms, but they are easily tolerated
Grade 2: Moderate	Enough discomfort to cause interference with usual activity
Grade 3: Severe	Incapacitating, with the inability to work or do usual activity
Grade 4: Fatal	Subject expired/death occurred

Table 2: Adverse Events Action(s) Taken

Action Taken	Description
(Check all that apply)	
None	No actions were taken, observation only.
Medications	Subject required medication(s)
Other Treatment	Subject required other treatment(s)
Early Withdrawal	Adverse event led to early study withdrawal

Table 3: Adverse Event Relationship to Hemodialysis or Study Procedure

Relationship	Description
None	Causal relationship can be ruled out
Possible – Hemodialysis	Causal relationship is reasonably possible to the hemodialysis procedure
Procedure	(i.e., the relationship cannot be ruled out)
Possible – Study	Causal relationship is reasonably possible to the protocol-required study
Procedure/Device	procedure and/or device (i.e., the relationship cannot be ruled out)
Yes – Hemodialysis	Causal relationship to the homodialusic procedure is cortain
Procedure	Causal relationship to the hemodialysis procedure is certain
Yes – Study	Causal relationship to the study procedure and/or device is certain
Procedure/Device	Causal relationship to the study procedure and/or device is certain

Table 4: Adverse Event Outcome

Outcome	Description
Recovered/Resolved	Subject recovered and event was resolved upon study completion
Recovered/Resolved with	Subject recovered but exhibited lingering minor symptoms upon
Sequelae	study completion
Recovering	Adverse event persisted upon study completion but was improving
Not Decovered	Adverse event persisted upon study completion and was not
Not Recovered	exhibiting any signs of improvement
Death	Subject expired
Unknown	Status of the adverse event was unknown upon study completion

CONFIDENTIAL Page 17 of 24

SPONSOR: ZMS

PROTOCOL: ZMS-1500-2021-Dialysis

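### Table 3 merges two causality questions into one five-level list with no level for both, so a device-related adverse event tabulation can be understated

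*Combined protocol and SAP*

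**What the plan says.** Section 8.1.1 lists relationship as one of four descriptors of an adverse event: events "are characterized by grading, actions taken, relationship to hemodialysis procedure or study procedure, and outcome". The scale is "Table 3: Adverse Event Relationship to Hemodialysis or Study Procedure", a single column with five levels: *None*, *Possible – Hemodialysis Procedure*, *Possible – Study Procedure/Device*, *Yes – Hemodialysis Procedure* and *Yes – Study Procedure/Device*.

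The possible-hemodialysis row reads "Causal relationship is reasonably possible to the hemodialysis procedure" and explains this as a relationship that has not been excluded. The possible-device row begins "Causal relationship is reasonably possible to the protocol-required study" and continues "procedure and/or device (i.e., the relationship cannot be ruled out". Table 2, on actions taken, tells the user to "Check all that apply"; Table 3 has no such instruction. Section 8.1.2 applies the same relationship coding to serious adverse events.

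On analysis, Section 8 says only that adverse events are reviewed and summarised. Section 9.3 gives categorical measures as counts and percentages.

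**The concern.** Whether dialysis could have caused an event and whether the device or study procedure could have caused it are separate questions, and the answer to one does not settle the other. Table 3 asks them as one.

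The overlap is built into the design. Under Section 5.3 the device is started at least 5 minutes before dialysis, worn through it, and kept on for 10 minutes afterwards. Subjects must also keep largely still (Section 4.2) and hold a supine or sitting position (Section 5.3.2). Section 7.1 names a study risk that fits both sources: "Discomfort could occur due to lying in a supine position for duration of the hemodialysis procedure".

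At stake is the device-related line of the adverse event summary. For non-serious or anticipated device events, Table 3 is the only place in the protocol where a link to the device is recorded.

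**Working it through.** The plan gives no adverse event rate and no device-related figure to reproduce. The check is of the structure of the table.

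**1. What two questions would yield.** With three answers to each (none, possible, yes) there are 3 × 3 = 9 combinations. Under single choice, Table 3 represents them as follows:

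| Hemodialysis | Device: none | Device: possible | Device: yes |
|---|---|---|---|
| none | *None* | *Possible – Study Procedure/Device* | *Yes – Study Procedure/Device* |
| possible | *Possible – Hemodialysis* | no level | no level |
| yes | *Yes – Hemodialysis* | no level | no level |

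Five combinations have a level; 9 − 5 = 4 do not. Those four are the events with two possible or certain causes.

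**2. Whether the rows exclude each other by definition.** They do not. Each *Possible* row asks only whether its own cause remains open. The device row does not require dialysis to be excluded first, nor the reverse. An event for which neither cause can be excluded meets both definitions, and nothing gives either row priority.

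**3. What a single choice loses.** A hemodialysis code does not say whether the device was excluded, and a device code does not say whether dialysis was. Once the event is coded, the other judgement cannot be recovered from Table 3.

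**4. Direction of the error.** Let M be the number of events with both causes open or certain, and p the share of them given a hemodialysis level. Assume that the underlying causal judgements are sound.

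- Shortfall in the device-related count = M × p.
- Shortfall in the hemodialysis-related count = M × (1 − p).

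An event with the device excluded does not qualify for a device row, and a two-cause event given a device level is already counted correctly. This mechanism therefore cannot raise the device-related count.

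**5. Size.** The documents give neither M nor p. For p from 0 to 1, the shortfall runs from 0 to M events. It cannot be narrowed further.

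**The case against.** The strongest reply is that single choice is never stated. The protocol nowhere limits Table 3 to one level, and the CRF, which would settle the matter, is not among the documents. That stands. The contrast with Table 2 makes single choice the natural reading, but it remains an inference. If several levels may be ticked, the loss disappears and only the missing instruction remains.

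It can also be said that no device-related count is defined, that this is a hypothesis-generating pilot of a cleared, non-invasive device, and that every event is recorded whatever its code. All of this is true and limits the importance of the point. But tabulating Table 3 under Section 9.3 yields a device-related line whether or not it is named. The event stays in the data; its possible link to the device does not.

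A reader might infer more than the documents support:

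- *That two-cause events will probably be coded to dialysis.* Such an event qualifies equally for the device row, and Section 7.1 lists supine discomfort among the study's risks, which could prompt the opposite choice.
- *That detection of unanticipated adverse device effects is biased.* Section 8.1.3 has the investigator flag these on the CRF and the sponsor evaluate them. Nothing makes that flag depend on Table 3. It covers only serious, unanticipated effects, so it does not replace Table 3 for other events.
- *That much of the event record falls on dialyses without the device*, because Section 5.5 covers events "that occur after informed consent and before completion of the study will be recorded". Participation ends with the third monitored session (Section 5.4), safety reporting ends with it (Section 8.2), and sessions are meant to be consecutive (Sections 2.3 and 5.4). A large off-device share would need missed sessions, which are the fallback.
- *That a rate can be attached to the loss.* Any such figure would rest wholly on assumed event counts and assumed coding.

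**Conclusion.** The point holds as a gap in the coding scheme. Table 3 puts two causality questions on one list, has no level for both and no rule for choosing, and does not say whether several levels may be selected. If one level is chosen and the causal judgements are otherwise sound, the device-related tabulation of AEs and SAEs can be understated but not overstated. The shortfall is between zero and the number of two-cause events, and the documents do not allow that number to be estimated.

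The primary and secondary objectives, which concern the Relative Index, are not affected. The change is worth making because it is nearly free and must be in place before events are coded.

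**What to change.** Replace Table 3 with two ratings, both completed for every AE and SAE:

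- relationship to hemodialysis: none, possible or yes;
- relationship to study procedure/device: none, possible or yes.

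State in Section 8 or 9 that an event is tabulated as device-related whenever the second rating is possible or yes, whatever the first rating is. Make the matching wording change in Section 8.1.2.

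The cost is one extra CRF field and a possibly higher device-related count. All present categories can still be derived.

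A smaller change would be to allow several levels in Table 3. That would capture two-cause events, but an unticked row would not show whether that cause was considered and excluded, so two ratings are preferable. A field for whether the device was on at onset is optional.

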4.4 SUBJECT WITHDRAW / EARLY TERMINATION

Subjects who withdraw from the study before using the CM-1500 device will be replaced. The reason the subject withdrew from the study may be recorded; subjects are not required to provide a reason. Subject withdrawal / early termination criteria may include but are not limited to:

- W.1 Subject requests to be withdrawn from the study or withdraws consent.
- W.2 Subject refuses or is unable to comply with required study procedures.
- W.3 An Adverse Event ("AE") makes the continuation of the subject impossible or inadvisable
- W.4 The Investigator determines it is in the subject's best interest to discontinue from the study.

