8.2 SAFETY REPORTING

Safety reporting begins at the time of signed Informed Consent and ends at subject study completion.

Investigators shall submit to the Sponsor a report of any AE's or SAE's that occur during the study within five (5) working days but no later than ten (10) days after the Investigator learns of the event.

Investigators shall submit to the Sponsor and to the reviewing IRB a report of any UADE(s) that occur during the study as soon as possible but no later than five (5) working days after the Investigator learns of the effect. Sponsors will evaluate UADE's.

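### Adverse event outcome is scored at study completion, so a non-serious event that outlasts the third session is recorded as unresolved or unknown with no planned later check

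*Combined protocol and SAP*

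**What the plan says.** Table 4 (section 8.1.1) has six outcome categories. All but death are defined by the event's state at study completion: for example "Subject recovered and event was resolved upon study completion" for recovered, "Adverse event persisted upon study completion but was improving" for recovering and "Status of the adverse event was unknown upon study completion" for unknown.

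Section 5.4 says when a subject reaches that point: "After the third CM-1500 monitoring session is complete, the subject's participation in the study is considered complete". Section 8.2 closes collection at the same moment: "Safety reporting begins at the time of signed Informed Consent and ends at subject study completion". After dialysis ends, section 5.3.3 tells staff to "continue the monitoring for a minimum of ten (10) minutes" before the session is stopped.

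The only later contact is in section 5.5: "SAE's may require follow-up contact via a telephone call, depending on the nature of the SAE". Nothing comparable exists for non-serious events. Section 8.1.1 asks sites to try to have events resolved by study completion, but sets no follow-up period.

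Section 4.4 (W.3) allows withdrawal because of an adverse event, and Table 2 lists early withdrawal as an action taken. Section 2.2 treats participation as complete when three sessions have not been done within 30 days.

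**The concern.** The time from onset to scoring is set by the session in which the event happens to fall. A session-1 or session-2 event can be looked at again at later sessions, within a participation that section 2.2 puts at about 1 to 2 weeks. A session-3 event has only the rest of that session. Two identical events lasting several hours can therefore receive different outcomes.

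Withdrawal because of an event leaves a second gap. Such a subject does not reach completion as section 5.4 defines it, and no section says when the outcome is then scored.

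Section 8 assesses safety by reviewing and summarizing adverse events, and outcome is one of the four attributes recorded for each. With 15 to 20 subjects and probably few events, one or two outcomes scored too early would visibly change the table. The reader could not tell which events had been followed for minutes and which for days.

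**Working it through.** The plan gives no figure on this point, so there is none to reproduce.

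**From the documents**
- Scoring time: study completion, in five of six Table 4 categories.
- Subject completion: end of the third monitoring session (5.4).
- Monitoring after dialysis: at least 10 minutes (5.3.3).
- Planned sessions: 15 completers × 3 = 45, of which 15 (33%) are third sessions. This is a share of sessions, not of events.

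**Assumed, because the documents are silent**
- Dialysis length L = 4 h (range 3 to 5 h).
- 48 h between monitored sessions.
- Onset uniform over dialysis, equally likely in each session, and never between sessions.
- Exponential time to resolution with median m, every event eventually resolving.
- Monitoring stopped 10 minutes (1/6 h) after dialysis.

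**Time available in session 3.** It runs from about 10 minutes (onset at the end of dialysis) to L + 10 minutes (onset at the start), that is 4 h 10 min for L = 4. Sessions 1 and 2 add 96 h and 48 h.

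**Share unresolved at scoring.** With λ = ln 2 / m,

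session 3: U3 = exp(−λ/6) × [1 − exp(−λL)] / (λL)

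session 2: U2 = U3 × 2^(−48/m); session 1: U1 = U3 × 2^(−96/m)

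With L = 4:
- m = 1 h: 0.891 × 0.338 = 0.301
- m = 6 h: 0.981 × 0.801 = 0.786
- m = 24 h: 0.995 × 0.944 = 0.940. Here 2^(−48/24) = 0.25, so U2 = 0.235 and U1 = 0.059.

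| Median duration | Session 1 | Session 2 | Session 3 (L = 4) | Session 3 (L = 5 to 3) | Mean of sessions (L = 4) |
|---|---|---|---|---|---|
| 15 min | 0% | 0% | 6% | 5–8% | 2% |
| 1 h | 0% | 0% | 30% | 25–37% | 10% |
| 6 h | 0% | 0.3% | 79% | 75–83% | 26% |
| 24 h | 5.9% | 23.5% | 94% | 93–95% | 41% |

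**With one update 48 h later for every event still ongoing.** Each share is multiplied by 2^(−48/m).
- m = 24 h: 1.5%, 5.9% and 23.5% for sessions 1, 2 and 3; mean (1.5 + 5.9 + 23.5)/3 = 10.3%, down from 41.1%.
- m = 6 h: the mean falls from 26% to about 0.1%.
- m = 1 h: it falls from 10% to about 0%.

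Updating only events that began in session 3 would do less: at m = 24 h the mean would be (5.9 + 23.5 + 23.5)/3 = 17.6%. The change should therefore cover all ongoing events.

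**What remains.** In this model the update multiplies all three sessions by the same factor, so the ratio of session 3 to session 1 is unchanged at about 16 to 1 (94.0/5.9 before, 23.5/1.47 after). The level falls; the dependence on session does not disappear.

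**The case against.** A reader might infer that recovery from a session-3 event cannot be scored at all. The documents do not support that. An event that resolves before the session is stopped is scored as recovered, and one that persists has its own category. At a 1 h median about 70% of session-3 events still count as recovered, and at 15 minutes about 94%. Nor does the outcome table simply mirror session number: that dependence is strong only for events lasting hours or longer. The 10 minutes is also a minimum, so a site that monitors longer loses less.

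A reader might also infer that every non-completer lacks an endpoint. Section 2.2 supplies one for the 30-day case, and the unknown category is always available. The gap that stands is narrower: no scoring time is stated for a subject withdrawn early because of an event.

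The strongest objection concerns the term itself. Table 4 says study completion without the word subject, section 6.3 uses the same words for the end of the whole study, and section 8.2 adds subject when it means the subject. If Table 4 means the whole study, most of the asymmetry could disappear, since the study is single-center and subjects return for dialysis anyway. But no contact or record review is planned to supply that later status, and section 8.2 has by then closed safety reporting. The general instruction in 8.1.1 to seek resolution creates no such contact either. The ambiguity is a further reason to define the term.

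Two limits stand. The figures rest on assumed durations and on in-session onset, whereas events are collected from consent onward, including between sessions. And this is a descriptive pilot with no planned comparison of outcome rates.

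**Conclusion.** The point holds in limited form. Read at subject level, the plan follows a non-serious session-3 event for minutes to hours and the same event in sessions 1 or 2 for days. Outcomes are then not comparable across sessions for events lasting hours or longer; for events lasting minutes the effect is small. For withdrawal because of an event, the scoring time is missing.

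The direction follows from the text alone. The size does not: 30%, 79% and 94% of session-3 events unresolved at medians of 1 h, 6 h and 24 h depend on the assumptions listed, and the documents give no event counts or durations to choose among them. The primary and secondary objectives are unaffected; only the descriptive safety summary is. This is an inexpensive improvement worth making, not a flaw that threatens the study.

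**What to change.** - **Table 4:** score the outcome at resolution or, if the event is ongoing at the subject's last monitoring session or withdrawal, once at the subject's next routine hemodialysis session. This defines the scoring time for completers and for withdrawn subjects, and removes the ambiguity in study completion.
- **Section 8.2:** state that new events stop being collected at completion or withdrawal, but that events already recorded and still ongoing are updated that one time.
- **Reporting:** list time from onset to last assessment beside each outcome, because the update lowers the difference between sessions without removing it.

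The cost is protocol wording, one CRF line and consent wording. No extra visit is needed, since subjects return for prescribed dialysis. The downside is that subjects with an ongoing event stay open for one more interdialytic interval, which the consent form must cover. The change concerns recording only, not care.
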